Time to collect specimens: Most participants in the community will only be studied once (demographic data, blood, skin snips, stool and urine samples). Thus, the **duration** of subject participation will be one day.

Parameters and criteria for assessing the impact of MDA:

Blood tests for *Wuchereria bancrofti* infection: The Binax Now Filariasis card test, the Alere Filariasis Test Strip, and the TropBio antigen test (with MF testing of antigen positive subjects). We are using

these tests as measures of LF endemicity. The antigen tests detect antigen released from living adult filarial worms potentially capable of resuming MF production in the future. The filarial antigen tests are much more sensitive for infection in treated subjects than tests for microfilaremia. However, antigen tests may remain positive for years after treatment has cleared microfilaremia. The antigen tests will be performed on blood from individual residents 5 years of age and older. This will be done by sampling populations in sentinel sites (villages) to produce N of 400-500 per site. There will be several sentinel sites for each treatment zone (annual vs. twice annual MDA). The sample size number per sentinel site is close to the overall minimum target sample size of 335 needed to show that the filarial antigen rates are less than 2% (with 95% confidence and 80% power, assuming an expected rate of 0.5%, which is an LF elimination target). While all subjects will be tested with the Binax Now Filariasis card test, not all blood samples will be tested with the Alere Filariasis Test Strip and the TropBio antigen test. The purpose of parallel antigen testing of a subset of blood samples is to compare the performance of these three filarial antigen tests.

Subjects with positive filarial antigen tests will be tested for microfilaremia with 60 µl night thick blood smears collected by finger prick at night. Night blood samples are needed for microfilaria detection, because the parasites only circulate in peripheral blood at night.

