With 4 years of annual cross-sectional surveys conducted by DOLF researcher and completed in both Maryland (last survey in 2016) and Lofa (last survey in 2017), we plan to conduct an additional one-time cross-sectional survey in the Harper site in Maryland district in 2019 and in Lofa (Foya & Kolahun Districts) in 2020 to measure the long-term impact of MDA on *W. bancrofti* (lymphatic filariasis), *O. volvulus* (onchocerciasis) and on STH infection parameters following these cumulative 7-9 rounds of MDA. Since the last DOLF surveys, there have been a total of 3 annual rounds of MDA in both areas.

The study will recruit 2,500 participants in the Maryland area villages and 3,200 in the Lofa area villages. The proposed activities will comprise of identical survey methods as previously conducted surveys in both study areas. The survey includes:

- ***Stool sample collection with Kato Katz analysis for STH infections,***
- ***Blood collection by finger prick during the day with analysis by FTS and thick blood smear for detection of *W. bancrofti* antigen and microfilaria (respectively) in the blood (TropBio antigen test and Binax Now card tests will not be used as they were found to be inferior to the Alere Test Strip (FTS))***
- ***Skin snips for detection of *O. volvulus* microfilaria in the skin***

As a final note, we will not provide MDA as part of this research, but we will share our findings to the MOH and others to support their decision-making for MDA continuation or cessation. We will publish the findings to support global policy decision making.

STUDY POPULATIONS

Description of human subject involvement in research:

We will perform repeated annual cross-sectional surveys in study communities. Eligibility: This project will study people who live in communities that are endemic or have been endemic at the beginning of the study for lymphatic filariasis (LF) and onchocerciasis (oncho). The LF endemicity rate (MF rate) should at the study begin should be about 10% and there should have been no MDA in area immediately prior to study begin. The prevalence of oncho is secondary, but should be at least 5% nodule rate or 10% skin MF. ***Eligibility criteria will remain the same in the continuation surveys in both areas.***

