20. 7.2 Sample Size Considerations

Except as otherwise noted, all sample sizes in this protocol were calculated using a binomial power calculator (using alpha = .05, two-tailed tests, and power = .80). These sample sizes were chosen to provide confidence that measured prevalence rates will be below specified limits based on assumptions regarding true prevalence rates. The sample size analysis considered various contingencies to assess robustness of the sample size estimates (see Appendix).

Note: Sample size considerations for community surveys for demonstrating that prevalence rates are below pre-defined targets for antigenemia, microfilaremia, microfiladermia, schistosomiasis, and STH infections are provided in Section 4, above, and this is not repeated here.

21. 7.3 Participant Enrollment and Follow-Up

This project aims to enroll at least 3,200 subjects per year in Foya District and 2,000 subjects per year in Maryland County. Study areas will have cluster surveys of approximately 400-500 people per 4 sentinel site (4 sites each in the annual and semiannual MDA areas). The community/household surveys are cross-sectional with no follow-up planned.

22. 7.4 Analysis Plan

The following outcome variables will be collected and treated as binary variables: Microfilaremia, microfiladermia, filarial antigenemia and antibody, and stool/urine parasites (separate analyses for *Ascaris*, *Trichuris*, schistosomes, and Hookworm). Microfilaria counts (recorded as MF/60 μ l blood), microfiladermia counts as MF/mg skin, nodules as nodules per person, and stool egg counts for each species (recorded as eggs/gram of feces or eggs/ml urine) will be taken as count variables.

Data will also be collected for demographic characteristics and covariates including age, gender, and history of lymphedema, scrotal swelling (hydrocele), and prior treatment for LF. For demographic characteristics variables, descriptive statistics will be examined for the individuals who participate in the trials by sentinel site (village) and over years of observation. Frequency will

be tabulated for categorical variables. Descriptive statistics (mean, median, range and standard deviation) will be obtained for continuous variables.

Impact of MDA on study outcome measures

1. Testing the primary hypothesis

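### Maryland's 2,000 participants a year do not fit eight sentinel sites of 400-500 people; they give about 250 per site, and the plan does not say whether its minimum of 335 applies per site or per zone.

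*Combined protocol and SAP*

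**What the plan says.** - **Enrolment (Section 7.3).** The aim is "at least 3,200 subjects per year in Foya District and 2,000 subjects per year in Maryland County". The Protocol Summary's total of about 5,200 a year agrees (3,200 + 2,000), so 2,000 does not look like a misprint.
- **Layout (Section 7.3, the next sentence).** Study areas, with no distinction between the two, have cluster surveys of "approximately 400-500 people per 4 sentinel site (4 sites each in the annual and semiannual MDA areas"). Section 7.4 also works with four sentinel sites in each treatment zone. Results of Previous Work reports both regimens in Maryland.
- **Size per site (Section 4).** Sampling is "to produce N of 400-500 per site".
- **Minimum (Section 4).** "The sample size number per sentinel site is close to the overall minimum target sample size of 335 needed" to show that antigen rates are "less than 2% (with 95% confidence and 80% power, assuming an expected rate of 0.5"%). Section 7.2 adds that calculations are binomial and two-tailed at 0.05, and refers back to Section 4 for the prevalence targets.
- **Continuation survey (Continuation Activities).** "The study will recruit 2,500 participants in the Maryland area villages and 3,200 in the Lofa area villages", using the same survey methods as before. The number of sites is not restated.

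**The concern.** Two adjacent sentences of Section 7.3 agree for Foya and disagree for Maryland. Nothing in the text gives Maryland fewer or smaller sites. A reader therefore cannot tell which is wrong for Maryland: the total, the number of sites, or the size per site.

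The sample-size justification for the antigen target is a comparison of the per-site number with 335. If Maryland's sites are about 250, that comparison does not describe Maryland. This is also the area where the question is most open. At the last surveys antigen positivity was 13% (semiannual) and 5% (annual) in Maryland, against 0% in both groups in Lofa. Section 2.2 expects the additional survey to determine whether the targets have been met, and the findings are to be shared with the Ministry of Health for decisions on continuing or stopping MDA.

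**Working it through.** **1. Reproduce 335.** Inputs from Section 4: rates 0.5% and 2%, 95% confidence, 80% power. An exact one-sample binomial test with 0.5% as null, 2% as alternative and upper-tail alpha 0.05 gives 335 as the smallest n with power of at least 0.80:

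- n = 335, reject at 5 or more positives: P(X ≥ 5 | 0.005) = 0.0277; P(X ≥ 5 | 0.02) = 0.8007.
- n = 334, same cutoff: power 0.7986.

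At n = 335, 5 positives also reject in the exact two-sided test (p = 0.0277) and 4 do not (p = 0.089), so this agrees with the two-tailed statement in Section 7.2.

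**2. People needed for the stated layout.** Sites per area = 4 + 4 = 8.

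- At 400-500 per site: 8 × 400 = 3,200 to 8 × 500 = 4,000.
- At 335 per site: 8 × 335 = 2,680.

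**3. People available.**

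| Survey | Total | Per site (÷ 8) | Per zone (÷ 2) |
|---|---|---|---|
| Foya, annual | 3,200 | 400 | 1,600 |
| Maryland, annual | 2,000 | 250 | 1,000 |
| Maryland, continuation, if still 8 sites and 2 zones | 2,500 | 312.5 | 1,250 |

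At the stated site size, 2,000 people fill 2,000/500 = 4 to 2,000/400 = 5 sites, not 8.

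**4. Power under the test from step 1.**

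| n | Reject at | Actual alpha | Power |
|---|---|---|---|
| 250 | ≥ 4 | 0.038 | 0.738 |
| 312 | ≥ 5 | 0.021 | 0.749 |
| 313 | ≥ 5 | 0.021 | 0.751 |
| 335 | ≥ 5 | 0.028 | 0.801 |
| 400 | ≥ 6 | 0.016 | 0.812 |
| 1,000 | ≥ 10 | 0.031 | 0.995 |

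The per-site shortfall is about 6 points at 250 and 5 points at 312-313.

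**5. Clustering.** The 335 reproduces with no design effect, and none is stated. A Maryland zone of 1,000 keeps an effective size of 335 as long as the design effect stays below 1,000/335 = 2.99. With 250 people per site and design effect = 1 + (250 − 1) × ICC, that limit is an intraclass correlation of 1.99/249 = 0.008. The documents give no value for it, so the margin at zone level is real but cannot be confirmed from them.

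**The case against.** **335 is not stated as a per-site requirement.** Section 4 calls it an overall minimum and says only that the per-site number is close to it. Section 7.4 plans no site-by-site test against 2%: it averages over the four sites of a zone, fits a mixed model, and uses the mean slope across villages to estimate time to target. This stands. At zone level Maryland has about three times 335. It does not remove the conflict between 2,000 people and eight sites of 400-500.

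**250 may be a floor.** The words for a minimum in Section 7.3 may govern the Maryland figure too. That is possible, but Maryland would need 1,200 more people (3,200 − 2,000) to reach 400 per site.

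**The site count may be what is wrong.** With four or five Maryland sites in all, the stated size per site would be right. Village counts do not settle this. Section 2.2 mentions 16 study villages, apparently Maryland's, and 26 in Lofa; Annex 1 mentions 32. None is eight, although Section 4 equates sites with villages. Section 7.2 also cites an appendix on sample-size contingencies that was not in the text available for review.

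**Eight sites in the continuation survey is an inference.** It rests on the statement that methods are unchanged. This stands, so 312 is conditional. Spread over 16 villages, 2,500 would be about 156 each.

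**A reader might infer a far larger loss of power** by taking 2% as the null and 0.5% as the alternative. That is not a like-for-like comparison with the plan's 80%. On that footing the plan's own 335 has only 50% power two-tailed and 76% one-tailed, so much of the gap belongs to how 335 was derived and not to Maryland. The exact test also moves in jumps there: n = 313 gives 79% one-tailed. Which hypothesis should be the null is a separate question.

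**Conclusion.** The concern holds as an internal inconsistency with a modest consequence. For the annual surveys, Maryland's stated total gives about 250 per site under the stated layout, against 400-500; Foya's total fits.

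What follows for 335 depends on a reading that the plan leaves open. Per site, Maryland is below it, with power of about 74% instead of 80%. Per zone, about 1,000 people exceed it, before clustering. For the continuation survey the corresponding figures are about 312 per site and 75%, but only if the eight-site layout is kept.

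A reader might go further and conclude that the below-2% claim fails in Maryland, or that the continuation survey cannot judge the target. The documents do not support that: they plan no per-site test, call 335 overall, and give no site count for the continuation.

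The power figures assume independent observations within a site, equal site sizes, and the exact test that reproduces 335.

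**What to change.** 1. In Section 7.3, give Maryland's number of sentinel sites and size per site separately from Foya's. Do the same for the continuation survey, and say how sites relate to the study villages (16 apparently in Maryland).
2. In Section 4, say whether 335 applies per site, per treatment zone or per study area.
3. Then do one of the following:
   - restate Maryland's per-site power (about 74% at 250; about 75% at 312 if eight sites are kept); or
   - state that in Maryland the below-2% antigen target is assessed at zone or area level, with a confidence interval adjusted for clustering and the assumed design effect given.

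The cost is wording and restated figures. No extra participants are needed. The first option puts a less favourable per-site figure on record; the second gives up any claim at the level of a single site.

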The primary hypothesis is that twice annual MDA is superior to annual MDA for eliminating LF. The binary outcome variables used to test this hypothesis include microfilaremia and antigenemia. The model which is being used will fit a linear trend over time within each village. The mean slope across villages within each treatment group will then allow estimates of time to target levels for control (microfilaremia < .5% and antigenemia < 2%) for a selection of baseline prevalences. To illustrate the analysis strategy, we use antigenemia as an example.

The antigenemia prevalence will be expressed as the filarial antigenemia rate (proportion of examined individuals with filarial parasite antigenemia detected with the Binax Now Filariasis card test. If Alere stops selling the card test, we may need to switch to their antigen strip test as the primary antigen test in later years of the project. To estimate the effect of MDA on antigenemia prevalence, we will tabulate mean rates of antigenemia across the four sentinel sites from each treatment zone (annual vs. twice annual MDA) over years of observation including the baseline. A generalized linear mixed model (GLMM) with a logistic link function will be used to account for the correlation of observations clustered within the same household from the same sentinel site. The model to estimate the difference in the odds of antigenemia includes treatment regimen and year of observation, and interaction between treatment regimen and year of observation. Some covariates that will be adjusted for in the analysis include sentinel sites, history of lymphedema, scrotal swelling (hydrocele) and prior treatment for LF as well as demographic variables of interest. Modeling will be performed with use of PROC GLIMMIX in SAS 9.2. CONTRAST statements will be used to test the significance of the log odds of antigenemia between the two treatment regimens at each year of observation. The difference of slope of rate decrease between the two regimens over the years of observations will also be tested with CONTRAST statements in PROC GLIMMIX. The resulting estimates will be converted to odds ratios with 95% confidence interval calculated from the robust estimator of variance. The other binary outcome variables (e.g., microfilaremia and microfilaridemia) will be analyzed with the same technique.

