With microfilaria (per 60 μ l of blood) measured as counts, we will display mean counts of microfilaria across the four sentinel sites from each treatment zone (annual vs. twice annual MDA) over years of observation including the baseline. To accommodate zero counts in modeling, we will use Geometric mean intensity (GMI) of circulating microfilaria. GMI is calculated as $\text{antilog}[(\sum \log(x+1))/n] - 1$, where x is the number of microfilaria per 60 mm^3 of blood and n is number of subjects. A generalized linear mixed model (GLMM) (implemented in PROC GLIMMIX) will be used to account for correlation of observations resulted from clustering. CONTRAST statements will be used to test the significance of differences in GMI of antigenemia between the two treatment

regimens at each year of observation. The resulting estimates of GMI will be presented with 95% confidence interval. All statistical tests will be two-sided at a significance level of 0.05, but one-sided p-value will be reported according to the hypothesis. Similar analytic models will be done for community Mf loads, community *O. volvulus* Mf load, and for community egg loads for each of three intestinal worm species.

The cost analysis comparing the two treatment regimens will be conducted by [name] of the George Washington University School of Public Health and Health Services. The model will also allow cost effectiveness analysis when combined with the efficacy analysis.

2. Testing secondary hypothesis

The secondary hypothesis is that twice annual MDA is superior to annual MDA for controlling STH and onchocerciasis in the Foya district. The primary endpoint for assessing the impact of MDA on STH infections is community egg load (average stool egg count per species). The primary endpoint for onchocerciasis will be Mf prevalence by skin snip. We will also compare community Mf loads for onchocerciasis. The analysis strategy for these end points is the same for microfilaria count in testing the primary hypothesis.

Adverse event

Since this is a minimal risk and nonintervention study, adverse events are not expected to be an issue. However, subjects will be monitored for adverse events related to blood collection. Proportion of subjects with an adverse event will be tabulated with 95% confidence interval for each sentinel site at each year of observation.

Treatment coverage rate

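### The primary superiority hypothesis is tested on two outcomes, at every year and on the slope, each at 0.05 with no decisive test; the chance of a false superiority finding is about 10–17% against a nominal 2.5%

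*Combined protocol and SAP*

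**What the plan says.** Section 7.4 (Analysis Plan, under the primary hypothesis) sets out a single directional claim: "The primary hypothesis is that twice annual MDA is superior to annual MDA for eliminating LF". It then attaches two outcomes to it: "The binary outcome variables used to test this hypothesis include microfilaremia and antigenemia".

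Two kinds of test are specified, with antigenemia as the worked example. The first will "test the significance of the log odds of antigenemia between the two treatment regimens at each year of observation". The second is the slope: "The difference of slope of rate decrease between the two regimens over the years of observations will also be tested with CONTRAST statements". Microfilaremia is treated alike: "The other binary outcome variables (e.g., microfilaremia and microfilaridemia) will be analyzed with the same technique".

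The section then adds yearly contrasts of geometric mean intensity (GMI) and sets the error level: "All statistical tests will be two-sided at a significance level of 0.05, but one-sided p-value will be reported according to the hypothesis".

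No section names a decisive outcome, year or contrast, requires both outcomes to succeed, or adjusts for multiple tests. Section 7.4 also says that a linear trend is fitted within each village and that mean slopes are used to estimate time to the control targets.

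**The concern.** A hypothesis with several tests and no rule for combining them can be declared supported when any one of them is significant. The 0.05 level then applies to each test but not to the primary conclusion. When outcomes, years and slope disagree, the plan gives no way to say which result counts.

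The yearly contrasts have a second weakness. They compare levels between zones, so a difference already present before MDA can appear as a regimen effect. The slope contrast is not affected by a constant difference between zones on the log-odds scale.

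The documents show why a settled rule would help. The results summary before Section 2.2 says annual treatment was superior. Section 3 says annual was as effective as semiannual. The last-survey antigen figures in that summary are 13% (semiannual) and 5% (annual) in Maryland, and 0% in both groups in Lofa. Section 4 says the findings will be published to inform global policy.

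**Working it through.** The plan states no overall error rate, so there is no figure to reproduce.

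**Inputs from the documents**
- Two binary outcomes; one contrast per year and one slope per outcome (Section 7.4).
- Two-sided 0.05 per test, which is 0.025 in the superiority direction (Section 7.4).
- Four sentinel sites per treatment zone (Sections 7.3 and 7.4).
- Four annual surveys (Section 4, continuation activities).

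**Assumptions**
- One of the four surveys is baseline; the text does not say.
- Between-year correlation of village results and between-outcome correlation are each 0.3 to 0.8. The documents give neither. Positive correlation between outcomes is expected because only antigen-positive subjects are tested for microfilaremia.
- Each test holds its own nominal level. Any further inflation from having few villages is left out.

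**Number of tests.** A pre-MDA difference is not evidence of superiority, so the main count leaves baseline out: 2 × (3 yearly + 1 slope) = 8. With the baseline contrast it is 2 × (4 + 1) = 10.

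**Reference case, independent tests**
- 8 tests, superiority direction: 1 − 0.975^8 = 18.3%; either direction: 1 − 0.95^8 = 33.7%.
- 10 tests: 1 − 0.975^10 = 22.4% and 1 − 0.95^10 = 40.1%.

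**Correlated case.** Trials were simulated under no regimen effect with normal village-level results, 4 against 4 villages, and t tests on 6 degrees of freedom for each yearly contrast and each slope. Year was handled either as separate levels or as a fitted line per village, because Section 7.4 describes a linear trend. Ranges cover correlations of 0.3 to 0.8.

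| Chance of at least one significant result | Year as separate levels | Year linear |
|---|---|---|
| 8 tests, false superiority, two-sided 0.05 | 12–17% | 10–13% |
| 8 tests, either direction | 23–31% | 19–25% |
| 8 tests, false superiority, one-sided p<0.05 | 21–29% | 17–23% |
| 10 tests, false superiority, two-sided 0.05 | 13–20% | 10–15% |
| 10 tests, either direction | 26–37% | 20–27% |

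A separate calculation with normal test statistics, correlations of 0 to 0.8, and three or four post-baseline contrasts gives 9–21% for false superiority at two-sided 0.05.

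**GMI contrasts.** These are not counted above. Three post-baseline ones would make 8 + 3 = 11 tests; if independent, 1 − 0.975^11 = 24.3% in the superiority direction.

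**After the fix.** One designated slope test gives 5% two-sided and 2.5% in the superiority direction. Two unadjusted slope tests would give 1 − 0.95² = 9.75% if independent. With Holm, the smaller p-value is compared with 0.025 and, if that succeeds, the larger with 0.05; the overall rate is at most 5%.

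**The case against.** The best reply is that the plan already points to the slope. Section 7.4 introduces the linear trend first and ties it to time to target, so the yearly contrasts could be read as description. If year is linear, all contrasts for one outcome depend on only two parameters, which limits the inflation. This stands in part: it explains the lower figures in the right-hand column. It does not remove the problem, because the yearly contrasts are expressly tests of significance and the slope comes in as an addition: "The difference of slope of rate decrease between the two regimens over the years of observations will also be tested".

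A second reply is that the comparison is over. The surveys ended in 2016 and 2017, and what remains is one further survey in each area. This also stands: naming a test now cannot restore the 0.05 level for data already seen. It can still fix how the results are presented.

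Third, nothing in the documents ranks antigenemia above microfilaremia. It is tested in all subjects, but Section 7.4 uses it only as an example, both outcomes have targets, and Section 4 warns that antigen can persist for years after microfilaremia clears. So the choice of a single outcome should not be presented as obvious.

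Two stronger readings are tempting. A reader might infer that the chance of a false superiority claim is 25–35%. Figures of that size mostly count significant results favouring either regimen, while the hypothesis runs one way; they approach false superiority only if one-sided p<0.05 is taken as success. A reader might also infer that the conflicting conclusions about annual MDA came from selecting among tests. The documents do not show this, and neither statement claims that twice-annual MDA is superior.

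**Conclusion.** The concern holds. Section 7.4 tests one superiority hypothesis in at least eight ways after baseline, each at two-sided 0.05, without a decisive test or multiplicity control. The chance of a false superiority finding is about 10–17% against a nominal 2.5%, or up to 20% if the baseline contrast is also counted. A significant difference in either direction has a chance of about 19–31%. If one-sided p<0.05 counts as success, false superiority is about 17–29%; the plan does not rule this out.

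The exact figures depend on the assumed correlations, the assumption that baseline is one of the four surveys, and how year enters the model. The direction does not: the rate is several times nominal in every setting examined. This is worth correcting, but it does not invalidate the estimates themselves.

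**What to change.** - Make the regimen-by-year slope contrast, already planned in Section 7.4, the decisive test of the primary hypothesis. It matches the plan's own time-to-target aim.
- Either name one outcome as primary and give the reason, or test both the antigenemia and microfilaremia slopes with Holm control at an overall two-sided 0.05.
- State that superiority is judged at two-sided 0.05, so that the reported one-sided p-value is not used as the criterion.
- Report year-specific and GMI contrasts as estimates with confidence intervals, without superiority claims.
- Disclose that the designation was made after comparative data were available, and still report every planned contrast.

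This needs new wording in Section 7.4 and the disclosure, but no new data or models. The sponsor gives up claiming superiority from an isolated year, and loses a little power if alpha is shared across the two slopes.

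### Regimen is constant within a village, but section 7.4 gives the regimen tests no village-level variance, robust clustering level or degrees of freedom, and compares coverage with a plain chi-square

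*Combined protocol and SAP*

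**What the plan says.** Sections 4 and 7.3 place several sentinel sites in each treatment zone, four per regimen. Results of Previous Work labels whole villages as annual or semiannual. Regimen therefore does not vary within a site.

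Section 7.4, on the primary hypothesis, begins at village level: "The model which is being used will fit a linear trend over time within each village", and "The mean slope across villages within each treatment group will then allow estimates of time to target levels for control". It then takes antigenemia as the worked example. A logistic mixed model will "account for the correlation of observations clustered within the same household from the same sentinel site", with terms for regimen, year and their interaction. It adds that "Some covariates that will be adjusted for in the analysis include sentinel sites", in the same list as hydrocele and prior treatment.

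Two kinds of regimen test follow. CONTRAST statements will "test the significance of the log odds of antigenemia between the two treatment regimens at each year of observation", and "The difference of slope of rate decrease between the two regimens over the years of observations will also be tested with CONTRAST statements". Odds ratios carry a "95% confidence interval calculated from the robust estimator of variance". The same technique serves the other binary outcomes. The count models mention clustering without naming a level.

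Under Treatment coverage rate, coverage is compared between regimens over time by chi-square, with no cluster adjustment stated.

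**The concern.** When regimen is constant within a village, the regimen comparison has as many independent units as there are villages. A standard error built on persons or households leaves out variation between villages. If villages differ, intervals are then too narrow and false differences between regimens are too frequent.

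Section 7.4 does not say which variation its regimen tests include. It states no village variance component, no level for the robust variance and no denominator degrees of freedom. The village-slope sentences are tied to time-to-target estimates, while the slope test is described separately as a contrast in the regimen-by-year model. For coverage, the named test has no place for villages at all.

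At stake are the tests of the primary hypothesis, the outcomes that reuse them, and the coverage comparison. Section 4 (Continuation Activities) says the annual surveys are complete, so this concerns analysis and reporting only.

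**Working it through.** **Inputs from the documents.** Section 7.3: 3,200 people per year in Foya, 2,000 in Maryland, four sites per regimen. Section 4: four annual surveys. Number of villages: four sites per zone in 7.3 and 7.4; 16 villages in 2.2 (Maryland, from context); 26 in Lofa in 2.2; 32 in Annex 1. People per village follow: 3,200/8 = 400; 2,000/8 = 250; 2,000/16 = 125; 3,200/26 = 123; 3,200/32 = 100. No figure in the plan tests this point, so there is none to reproduce first.

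**1. Coverage chi-square.** With m people per village, the design effect is DE = 1 + (m − 1) × ICC. The true type I error of a nominal 5% test that ignores it is 2 × [1 − Φ(1.96/√DE)]. The ICC is assumed.

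| m | DE at ICC 0.01 | Error at ICC 0 | Error at ICC 0.01 |
|---|---|---|---|
| 100 | 1.99 | 5% | 17% |
| 125 | 2.24 | 5% | 19% |
| 250 | 3.49 | 5% | 29% |
| 400 | 4.99 | 5% | 38% |

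**2. Yearly contrasts with sites as fixed effects.** Eight site columns + regimen + year + regimen × year = 11 columns, with rank 10, because regimen is a sum of site columns. A regimen contrast without site coefficients is non-estimable in all four years. It becomes estimable when averaged over sites, but then describes only these villages. The slope contrast is estimable either way. If sites were left out and no village variance were added, the errors in step 1 would apply to the yearly contrasts too.

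**3. Slope test.** Simulation with no regimen effect, 4,000 replicates per scenario. Assumed: common slope −0.4 logit/year, village intercept SD 0.4, households of 4. Ranges span baseline prevalence 10-25% and household SD 0.5-1.0. The model has fixed sites and a household-robust variance. Entries are type I error by assumed SD of village slopes (logit/year).

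| Villages per zone × people | SD 0 | SD 0.05 | SD 0.1 |
|---|---|---|---|
| 4 × 400 | 5% | 9-12% | 17-29% |
| 4 × 250 | 5% | 7-10% | 13-22% |
| 8 × 125 | 5-6% | 6-7% | 9-14% |
| 13 × 123 | 5% | 6-8% | 9-14% |
| 16 × 100 | 5-6% | 6-7% | 8-13% |

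- Fixed village slopes at SD 0.1: 13-28% with 4 per zone, 9-13% with 8-16.
- Steep decline (slope −1.0, from 10% to 0.55% by survey 4; 2,000 replicates), SD 0.1: 8-11% with 4 per zone, 6-8% with 8-16.
- Two-stage t-test of village slopes (Firth fit, 2K − 2 df, K villages per zone): 4-6% in the main scenarios, 3-6% under steep decline.
- Village-clustered robust variance, 4 per zone: 13-17% with a normal reference, 7-10% with t on 6 df.

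A full three-level mixed model was not simulated, and no zone-level variance was included.

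**The case against.** The strongest reply is that section 7.4 opens with a trend in each village and a mean slope across villages, then presents the mixed model as an illustration of that strategy. Read as random slopes or a two-stage analysis, the slope test accounts for village differences. This stands: for the slope test the defect is missing specification. It does not reach the yearly contrasts or the coverage chi-square.

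Second, every inflation figure rests on an assumed ICC or slope SD, and at zero village variation there is essentially no inflation. Results of Previous Work reports 0% antigen positivity in both Lofa groups in 2017, so for Foya antigenemia the steep-decline figures fit better than the main ones. This also stands.

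Third, site-averaged yearly contrasts have no inflated error for the villages actually studied. That is true, but the plan's hypothesis is about regimens in general, and the choice of contrast is not stated.

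Fourth, coverage is a process measure rather than a trial hypothesis. That lowers the stakes, but the comparison is still between regimens and the test still ignores villages.

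A reader might go further and infer that the regimen analyses did ignore villages, or that the 2016 Maryland antigen gap (13% semiannual, 5% annual) is an artefact. The documents support neither: they report no test, sample size or ICC for that gap, and do not say how the models were fitted.

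**Conclusion.** The point holds as an omission for the section 7.4 regimen contrasts and as an error for the coverage test.

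- **Coverage:** the chi-square is wrong as written whenever villages differ, with true error of about 17-38% at an assumed ICC of 0.01, depending on village size.
- **Slope test:** valid under a random-slope or two-stage reading. Under household-based or fixed-slope inference, error is about 8-29% at an assumed slope SD of 0.1 logit/year, and nearer 6-11% if prevalence falls as steeply as Lofa suggests.
- **Yearly contrasts:** with fixed sites, software would flag the plain contrast as non-estimable. The consequence is an unplanned choice of contrast, not a false p-value.

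Confidence is high in the omission. The size of any harm is conditional, because the documents give no ICC or slope SD and do not settle the number of villages. Across 4 to 16 villages per zone, 2K − 2 runs from 6 to 30 degrees of freedom.

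**What to change.** Make the village the unit of inference for every regimen comparison, and state the number of villages per zone (K).

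- **Slope test:** tie the village trends in 7.4 to the test. Use either a two-stage t-test of village slopes on 2K − 2 df, with a bias-reduced fit for zero counts, or random village intercepts and year slopes with small-sample df. The mixed model may be unstable with eight villages. If one of these was already intended, say so and give the df.
- **Yearly contrasts and count or geometric-mean models:** compare village-level summaries, covariate-adjusted if wanted, by t-test on 2K − 2 df, or use random village and village-by-year effects. Do not enter site as a fixed effect in the yearly contrasts; it may stay for the slope contrast.
- **Robust variance:** name its clustering level, and do not rely on an uncorrected village-level version with only eight villages.
- **Coverage:** replace the chi-square with a comparison of village coverage rates.
- **Limits:** state that none of this removes confounding of regimen with zone.

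The cost is SAP wording and re-run code, with no new data. If village slopes do not differ, slope-difference intervals are about 20% wider with 4 villages per zone and about 6-11% wider with 16. If they do differ, intervals widen more: with 4 × 400 per zone, the median half-width goes from 0.11-0.16 at slope SD 0 to 0.19-0.23 at SD 0.1.
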